SENSITIVITY TO INSULIN	Insulin's ability to promote glucose uptake by muscle tissue, and suppress glucose production by the liver and avoid the lipolysis in adipose tissue.	It will be evaluated using Matsuda's index with glucose and insulin values during CTOG using the following formula: Insulin sensitivity = $\frac{10000}{\sqrt{(G_0 \times I_0) \times (\bar{G}_{0-120} \times \bar{I}_{0-120})}}$	Quantitative	Reason	Natural numbers

CARDIO-VASCULAR FUNCTION	Function of the system made up of heart and blood vessels for transport activities.	Measurement of ejection fraction, diastolic and systolic preloads and ejection fraction.	Quantitative	Continues	Percentage %
--------------------------	---	--	--------------	-----------	--------------

METHODS.

Identification of patients at risk

During this initial phase, overweight or obese patients will be identified with and at least 2 risk factors for DM 2, who will be invited to the screening of the study and as a first step will answer a survey of nutrition and physical activity.

Recruitment of patients

Metabolic evaluation and classification of patients: Once obtaining weight and size, we identify overweight or obese patients and risk factors for DM2, they will be invited to continue the counting phase; The next step will be to cite patients for fast glucose measurement, and only patients who have a glucose level of 100mg/dL will have CTOG performed to determine the presence of prediabetes.

Glucose tolerance curve: The tolerance curve consists of citing the patient with an 8-12 hrs fast, the vein is channeled to the ulnar with 0.9% 250cc saline solution, basal blood samples are taken and 75g of glucose is given to drink and subsequently take blood samples every 30 minutes for the next two hours (0, 30, 60, 90 and 120min), for glucose determination at that time and for subsequent measurement of insulin, glucagon and GLP-1. As mentioned in the selection criteria, patients who are diagnosed with DM2 during screening (CTOG) will not be included in the study.

According to glucose values within 2 hours of oral loading, patients will be classified as:

- 1) Glucose-tolerant norms when glucose at 2hrs during CTOG is <140mg/dl,
- 2) Patients with glucose intolerance when glucose at 2hrs of CTOG is between 140 and 199mg/dL,

3) Recently diagnosed DM2 patients when glucose is 2 hrs. CTOG is 200mg/dL.

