Patients with CTOG glucose intolerance are those who will be invited to participate in the trial and those who accept will continue with a more thorough metabolic evaluation. For this purpose, patients will have completed a medical history and the following studies:

1) Fasting basal blood samples for measurement of:

- Blood count
- Lipid profile
- Insulin for homa-IR determination, HOMA-B, insulin sensitivity, insulin secretion and pancreatic beta cell function.

2) Determination of body composition (% visceral fat, % total body water, bone mineral density, etc.) using DEXA analysis. Here the patient scrutiny ends and if at this time the patient agrees to participate in the phase of intervention, the following will be carried out, after explanation and signature of informed consent letter.

- 1) Cardiovascular function assessment: This will be done through standard echocardiography area of the High Specialty Regional Hospital.
- 2) Evaluation of renal function: Through 24-hour urine collection, which will measure creatinine clearance and 24-hour albuminuria.
- 3) Randomization: It will be done by using a table of random numbers generated by a computer program. Patients will be randomized to receive, for 6 months, one of the following 2 interventions: 1) Dosis of *linagliptin 2.5 mg* every 24 h + *metformin 1700 mg* every 24 h y 2) 1 tablet every 12 h of Metformin 850mg.

THIRD PHASE: *Intervention and follow-up*

All patients will receive nutritional guidance and physical activation during the study. Once patients have all baseline measurements and have met the selection criteria, they will be randomized to one of the two interventions. All patients will have monthly follow-up and global clinical evaluation and treatment attachment, and anthropometry.

FOURTH PHASE: *Ending of the study (final measurements)*.

At 6 months of treatment, patients will be quoted again in fasting, on two different occasions,

- 1) FIRST APPOINTMENT: For measurement of glucose and fasting insulin, determination of body composition by imdoanciometry and performance of CTOG.
- 2) SECOND APPOINTMENT: Evaluation of cardiovascular function by echocardiography, and renal function by depurating creatiline and albumin in urine of 24h.

STATISTIC ANALYSIS

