The data will be presented with descriptive statistics, mean and standard or median deviation and interquartile travel, as well as percentages and incidence. For comparisons of numeric variables between study groups, we will use Student t if the distribution of the data follows a normality pattern, otherwise the Mann-whitney U test will be used; to compare qualitative variables we'll use square Chi. Analysis by intent to be treated and analyzed by protocol shall be performed and considered as significant when the p-value is <0.05. For the analysis and presentation of the data we will use the sPSS Version 15 and GraphPad Prism program 5.

ETHICAL ASPECTS

Ethical standards, Regulations of the General Health Law on Health Research and the Helsinki Declaration of the World Medical Association of the 64th General Assembly, StrongHold, Brazil in 2013 and current international codes and standards of good clinical research practices. Special attention will be given to taking care of the privacy and

autonomy of the patient. Once the patient has been informed about the study and agrees to participate in it, and since it involves a greater risk to a minimum, the signature of informed consent letter will be requested.

BIBLIOGRAPHIC REFERENCES:

4. Villalpando S, de la Cruz V, Rojas R, Shamah-Levy T, Avila MA, Gaona B, et al. Prevalence and distribution of type 2 diabetes mellitus in Mexican adult population: a probabilistic survey. *Salud Publica Mex* [Internet]. 2010 [cited 2018 Apr 7];52 Suppl 1:S19-26. Available from: <http://www.ncbi.nlm.nih.gov/pubmed/20585724>

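### The only consent signature with a stated place comes after the glucose tolerance test, research bloods and DEXA, and no screening consent is described

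*Combined protocol and SAP*

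**What the plan says.** Under Methods, Identification of patients at risk, overweight or obese people with risk factors are those "who will be invited to the screening of the study and as a first step will answer a survey of nutrition and physical activity". Under Recruitment of patients, after weight and height, "The next step will be to cite patients for fast glucose measurement". The CTOG is restricted: "only patients who have a glucose level of 100mg/dL will have CTOG performed to determine the presence of prediabetes" (a comparison sign appears to have been lost before the figure).

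The Glucose tolerance curve paragraph describes an invasive test: "the vein is channeled to the ulnar with 0.9% 250cc saline solution, basal blood samples are taken", followed by 75 g of glucose and sampling at 0, 30, 60, 90 and 120 minutes. The blood serves both the immediate glucose reading and later assays of insulin, glucagon and GLP-1.

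People found to have glucose intolerance are then invited to the trial. Those who accept go on to a medical history, fasting bloods and body composition "using DEXA analysis. Here the patient scrutiny ends". At that point comes the only signature with a place in the sequence: if the patient agrees to "participate in the phase of intervention, the following will be carried out, after explanation and signature of informed consent letter". The items listed after it are echocardiography, 24-hour urine for creatinine clearance and albuminuria, and randomisation.

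Two other sections mention the letter. The selection criteria require it but give no timing. Ethical Aspects says that, once the patient has been informed and has agreed, and "since it involves a greater risk to a minimum, the signature of informed consent letter will be requested". In the translated text this reads as rating the study above minimal risk.

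**The concern.** A site that followed the written order would cannulate a vein, give a glucose load, draw five timed samples, keep blood for research assays and carry out a DEXA scan before explaining the study and obtaining a signature. The explanation is placed late as well as the signature.

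These steps go beyond what screening needs. The protocol classifies patients by the 2-hour glucose alone. The insulin values feed the study's own outcomes (the Matsuda index and the 0-30 minute insulin-to-glucose ratio), and DEXA serves the body-composition objective.

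What is at stake is first the protection of the people screened, and second the standing of the baseline data, since the same CTOG supplies the start-of-study values. Neither can be put right after the procedures have been done.

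**Working it through.** No formula in the plan bears on this point. The check is to put the steps in the order in which the Methods section gives them and see who reaches each one.

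| Step | Who has it | Relative to the described signature |
|---|---|---|
| Survey, weight and height | People invited to screening | Before |
| Fasting glucose | Those invited to continue | Before |
| Cannulated CTOG, samples kept for hormones | Those who pass the fasting glucose step | Before |
| Medical history, fasting bloods, DEXA | Those with glucose intolerance who accept the invitation | Before |
| **Explanation and signature** | Those who agree to the intervention phase | n/a |
| Echocardiography, 24-hour urine | Those who signed | After |
| Randomisation | Those who signed | After |

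**Does another section move the signature earlier?** The selection criteria make it a condition of entry without a time. Ethical Aspects ties it to being informed and agreeing to participate, but not to any procedure. Neither overrides the one place where a time is given.

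**Is the screening CTOG also the baseline?** The specific objectives call for insulin resistance and beta-cell function at the start and at 6 months, and for the glucose curve at baseline and end. No second CTOG is described between the signature and randomisation, so the screening test has to supply these values.

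**Which outcomes are affected?** The protocol lists four dependent variables.
- Insulin sensitivity: CTOG-derived, baseline before the signature.
- Beta-cell function: CTOG-derived, baseline before the signature.
- Glucose homeostasis: defined as a yes/no status at 6 months, so the variable itself has no baseline value. The baseline curve serves eligibility and the descriptive objective on glucose metabolism.
- Cardiovascular function: baseline echocardiography after the signature.

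That makes two of the four, plus the DEXA data.

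**How many people?** Planned participants: 17 per group × 2 = 34, all with baseline CTOG and DEXA before the described signature. The documents do not say how many CTOGs are needed to find them. As an illustration only, assume that between 1 in 2 and 1 in 4 of those tested have glucose intolerance, and that all of them are randomised:
- 34 / 0.50 = 68 tests, of which 68 − 34 = 34 people leave without reaching the signature
- 34 / 0.25 = 136 tests, of which 136 − 34 = 102 people leave without reaching it

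This range concerns the CTOG only; these people do not reach DEXA. Refusals after a qualifying CTOG would add to it.

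**The case against.** The strongest reply is that the text does describe agreement along the way. People are invited to screening, invited to continue, and must accept a further invitation before the fasting bloods and DEXA. The signature is tied to the intervention phase, which leaves room for a separate screening letter. Consent pages were not in the copy reviewed, so such a letter cannot be ruled out. Everyone randomised has signed by then, so the selection criterion is met.

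Much of this stands. A reader might infer that procedures are done without any consent; the documents support only that no written consent is described before them. A reader might also infer a contradiction with the selection criteria, but a letter signed before randomisation satisfies them.

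The core remains. The acceptance that the text mentions before the fasting bloods and DEXA comes after the CTOG, so it cannot cover that test, and no signature is attached to it. If a screening letter exists, the step-by-step text is where a site would need to find it, and it is not mentioned there.

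**Conclusion.** The point holds as a matter of stated order. The only explanation and signature given a place in the protocol follow the CTOG, research bloods and DEXA, and no screening consent is described. It affects everyone given a CTOG, and the baseline insulin sensitivity, beta-cell and DEXA data of all 34 planned participants. Ethical Aspects does not contradict the order outright, because it names no procedure. But asking for a signature on grounds of risk fits poorly with obtaining it after most of the invasive baseline work. The order should be corrected before recruitment.

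Three stronger readings are not supported:
- That every screened person has all these procedures. The fasting glucose step limits who has the CTOG, and glucose intolerance plus acceptance limits who has the bloods and DEXA.
- That the baseline data would be unusable. Nothing in the documents says that an ethics committee would bar them or that the later letter excludes screening data. The planned comparisons between groups at the end of the intervention need no baseline value; only the start-and-end objectives would be exposed.
- That all baseline data, or three of the four dependent variables, are affected. Echocardiography and renal measures follow the signature, and glucose homeostasis is a 6-month status.

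The conclusion rests on the procedural text as it stands and on there being no screening letter outside it. The 34 to 102 screen failures depend on an assumed yield. No sample size, power or test result changes.

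**What to change.** Amend Recruitment of patients and the metabolic evaluation text so that explanation and written consent come before the first study-specific procedure. This can be one letter covering screening and intervention, or a short screening letter with the existing intervention letter kept where it is. After DEXA, leave only a confirmation that the patient is still willing to be randomised. Align the selection criteria and Ethical Aspects by stating in each when the letter is signed. If a screening letter already exists, cite it at the start of the sequence and say that it covers the CTOG, the stored samples for hormone assays and DEXA.

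The cost is a short amendment and additional signatures from people who fail screening. No test is added and the analysis is unchanged.

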low doses, can have a greater impact on the progression of the disease and reduce the cardiovascular risk that occurs since prediabetes.

JUSTIFICATION

DM2 is a chronic disease that has reached the proportions of a global epidemic from the increasing number of patients in all countries; has become the disease that causes the most chronic and acute complications to patients, consuming a large percentage of health spending in countries such as Mexico, it generates a large number of disabilities in productive ages and is one of the main causes of cardiovascular morbidity. The pathophysiology of the disease is complex and multifactorial, with great influence of the environment that the appearance of pathophysiological phenomena that as manifestation intermediation have hyperglycemia, and as a final manifestation, complications; and it is precisely the sequence of pathophysiological events that gives the disease a continuous spectrum in the natural history of it, unfortunately, when the diagnosis of DM2 is made we are identifying patients in very advanced stages of the disease, at which point up to 50% of them may have any of the known complications, and this together with the fact that we do not have a good diagnostic tool and that most patients with DM2 are outside the goals of cardiometabolic control, explains the great significance, exponential growth and difficulty that has conferred on health systems to control it. For all of the above, it seems clear that the best strategies will be those that are aimed at the early stages of the disease, because it will involve more awareness in the population and the impact on the stability and/or reversibility of the pathophysiological alterations, which will eventually translate into a lower incidence DM2. The studies on prevention of DM2 that have been conducted have not compared the effect of some of the drugs that have so far been more effective for this purpose and in some of these studies the doses used are frequently associated with the appearance of side effects; of these studies, none have been conducted in Mexico, and we are convinced that if we use the combination of drugs with additive pathophysiological impact plus cardiovascular protection in early stages, we can obtain better, longer-lasting and more impactful results on the natural history of the disease with a view to long-term follow-up that shows measures that may have an applicability in clinical practice, in order

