Type of Study: Clinical trial (randomized, controlled and triple-blind).

MATERIAL AND METHODS.

Study universe: Mexican patients with prediabetes and overweight/obesity.

Study population: Mexican patients with prediabetes and overweight/obesity, from the State of Guanajuato.

Place of realization: Hospital Metabolism Laboratory of Division of Health Sciences of the University of Guanajuato, León, Gto.

Type of sampling: Non-probabilistic, of consecutive cases.

Sample size: The calculation of the sample size was based on the formula for comparing proportions. We hope that the low-dose combination of linagliptin + metformin will improve the outcome variables (insulin resistance, pancreatic beta cell function and cardiovascular function) by at least 75%, metformin use alone achieves this only by 30%(44.46), so the study is designed to detect a minimum difference of 45% between study groups with a type I (alpha) error of 0.05 and a sample power of 80% , and according to the following formula(70):

$$n = \frac{(Z\alpha/2 + Z\beta)^2 p^- (1-p^-)(r + 1)}{(d)^2 r}$$

Where,

$$(Z\alpha/2 + Z\beta)^2 = 7.9$$

p^1 = proportion of individuals in the best treatment who failed to achieve improvement = 0.25

p^2 = proportion of individuals in the worst treatment who failed to achieve improvement = 0.70

r = reason for individuals in treatment groups = 1

d = difference you're expected to find = 0.45

n = 14 + 20% of losses = 17 patients per group

SELECTION CRITERIA TO PARTICIPATE

- Women and men aged 18 to 65 overweight or obese (BMI 25 kg/m²)
- Patients with prediabetes, defined by:
 - 1) Glucose intolerance (ITG = glucose at 2h en la CTOG between 140-199mg/dL).

2) The coexistence of fasting impaired glucose (GAA = fasting glucose between 100 and 125mg/dl) and glucose intolerance (ITG = glucose at 2h in CTOG between 140-199mg/dL).

- Those who agree to participate in the study sign an informed consent letter.

NOT SELECTED TO PARTICIPATE

- Patients with DM2 previously diagnosed or detected during sampling and CTOG.
- People currently being treated or for the past 3 months with metformin, pioglitazone, or any other antidiabetic drug, including insulin.
- Serum creatinine >1.6mg/dl.
- Very high hipertriglyceridemia (>500mg/dl).
- Pregnant women.
- Uncontrolled arterial hypertension (systólic >180mmhg o diastolic >105mmHg).
- Excessive alcohol intake, acute or chronic.

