- Medications or medical conditions affecting glucose homeostasis (thiazides, beta blockers, systemic glucocorticoids, weight-reducing or anorexigenic drugs, Cushing syndrome, thyrotoxicosis)

ELIMINATION

- Intolerance to the medicine used.
- Absence to more than 20 % of follow-up appointments.
- That they do not finalize the study and monitoring protocol.

VARIABLES

INDEPENDENT VARIABLES

- 1) *Intervention*

DEPENDENT VARIABLES

- 1) *Glucose homeostasis.*
- 2) *Sensitivity to insulin.*
- 3) *Pancreatic beta cell function.*
- 4) *Cardiovascular function.*

OPERATION OF VARIABLES, MEASUREMENT SCALES AND MEASUREMENT UNITS.

DEPENDENT VARIABLE	CONCEPTUAL DEFINITION	OPERATIONAL DEFINITION	CLASIFICATION	MEASURE- MENT LEVEL	INDICATOR
INTERVENTION	It is the established therapeutic strategy to prevent the progression of Prediabetes to type 2 diabetes mellitus and its complications.	
A. Administration of 1 tablet of linagliptin 2.5 mg /metformin 850 mg every 24 hours + 1 tablet of metformin 850 mg every 24 hours.
 
B. Administration of 1 tablet of metformin 850 mg every 12 hours.
	Qualitative	Nominal	
A. Group with low dose treatment of Linagliptin/ Metformin.
 
B. Metformin treatment group.

DEPENDENT VARIABLE	CONCEPTUAL DEFINITION	OPERATIONAL DEFINITION	CLASIFICATION	MEASUREMENT LEVEL	INDICATOR
FUNCTION OF THE PANCREATIC BETA CELL	Pancreatic beta cell's ability to secrete enough Insulin to keep blood glucose levels at normal levels.	Value obtained by the CTOG, when applying the formula $(\Delta I_{0-30})/(\Delta G_{0-30})$, (ΔI_{0-30}) = difference in insulin value measured at 0 and 30 minutes. (ΔG_{0-30}) = difference in glucose value measured at 0 and 30 minutes.	Quantitative	Reason	Pmol/mmol,
HOMEOSTASIS OF GLUCOSE	Ability of therapeutic interventions to reverse glucose intolerance.	It shall be considered as YES when the fasting glucose level at 6 months after the intervention begins, either at 2 h during CTOG is <140mg/dL, and NO when glucose levels at 2h during CTOG are 140mg/dL.	Qualitative	Dichotomous Nominal	Yes No

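### Adverse events and intolerance are not an outcome in either arm, and intolerance appears only as an elimination criterion that is not reconciled with intention-to-treat

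*Combined protocol and SAP*

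**What the plan says.** - **Objectives.** The general and specific objectives cover insulin resistance, beta-cell function, cardiovascular function and risk markers, glucose metabolism and body composition. The secondary objectives are adherence, incidence of type 2 diabetes, and renal function. None concerns adverse events.
- **Variables.** The four dependent variables are glucose homeostasis, insulin sensitivity, beta-cell function and cardiovascular function.
- **Elimination.** The first of three criteria is "Intolerance to the medicine used". The other two are missing more than 20% of follow-up appointments and not completing the study.
- **Third phase (intervention and follow-up).** "All patients will have monthly follow-up and global clinical evaluation and treatment attachment, and anthropometry". The fourth phase adds the glucose tolerance curve, body composition, echocardiography and renal tests at 6 months.
- **Statistic analysis.** Intention-to-treat and per-protocol analyses are both planned. Neither set is defined, and no safety table or safety population is mentioned.
- **Ethical aspects.** Written consent is required "since it involves a greater risk to a minimum", which reads as a rating of more than minimal risk.
- **Background.** Metformin is described as the only drug approved for prediabetes. Linagliptin's stated indication is uncontrolled type 2 diabetes, and studies of incretins in prediabetes are said to be few.

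**The concern.** The experimental arm differs from control by one added drug, given to people without diabetes and outside the indication that the background states for it. A conclusion in favour of the combination would rest on metabolic and cardiac markers, with no planned account of what the added drug cost patients.

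The plan recognises one tolerability event and treats it as a reason to leave the study. If intolerance differed between arms, that difference would be a result of treatment. Under the plan it would surface, if at all, as unequal losses. Events that are not recorded during the 6 months cannot be recovered at analysis, so this has to be settled before data collection.

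**Working it through.** The plan gives no adverse-event or intolerance rate, so there is no safety figure to reproduce. The check asks whether any part of the plan would yield a comparison of events by arm, and what such a comparison could show at the planned size.

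**1. Tracing an intolerance event through the plan.** A patient develops intolerance in month 2.
- The monthly visit has a clinical evaluation with no listed event, date, severity or action.
- The elimination rule applies.
- No dependent variable or objective takes the event as a value.
- The analysis section compares numeric variables by Student t or Mann-Whitney and qualitative variables by chi-square, but no such variable holds the event.
- Intention-to-treat might keep the patient in the denominator for efficacy outcomes. It does not create a tolerability outcome.

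The event therefore reaches no planned table.

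**2. Sample size used.** The plan states 14 per group plus 20% losses: 14 × 1.2 = 16.8, rounded to 17. The allowance is 17 − 14 = 3 patients per arm. (The printed formula with the printed inputs gives 7.9 × 0.475 × 0.525 × 2 / 0.45² = 19.46, so 20 rather than 14. That is a separate matter. The planned 17 and 14 are used here.)

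**3. Upper bound when no event is seen.** The one-sided 95% bound is 1 − 0.05^(1/n).
- n = 17: 1 − 0.05^(1/17) = 0.162.
- n = 14: 1 − 0.05^(1/14) = 0.193.

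**4. Chance that at least one event occurs among 17 patients in an arm.** This is 1 − (1 − p)^17, where p is an assumed true rate:

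| Assumed p | Probability |
|---|---|
| 1% | 16% |
| 5% | 58% |
| 10% | 83% |
| 15% | 94% |

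These are chances that an event happens, not that it is recorded.

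**5. Power to compare arms, 17 per arm, two-sided 0.05.** Exact enumeration over all pairs of binomial counts, with assumed rates. The last column uses the normal-approximation formula for two proportions:

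| Control vs combination | Chi-square | Fisher | n per arm for 80% power |
|---|---|---|---|
| 5% vs 20% | 23% | 12% | 76 |
| 10% vs 30% | 30% | 19% | 62 |
| 20% vs 40% | 23% | 14% | 82 |

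**6. What an imbalance in eliminations would look like.** Fisher's two-sided p for k eliminations against 0, with 17 per arm:
- 3 vs 0 (the whole loss allowance in one arm): p = 0.23
- 4 vs 0: p = 0.10
- 5 vs 0: p = 0.044

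A one-sided pattern of intolerance could pass as ordinary dropout unless eliminations are listed by arm and reason.

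**The case against.** Several points count against the concern, and some of them limit it.

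- **Intention-to-treat is planned.** A reader might infer that intolerant patients vanish from every analysis. The documents do not support that. Removal is clear only for the per-protocol set, and nothing forbids reporting eliminations by reason. What stands is that the two provisions are not reconciled, and that intention-to-treat decides who is counted for an outcome without supplying the missing outcome.
- **Some safety-related data are collected.** Creatinine clearance and albuminuria, diabetes incidence and adherence are secondary objectives by group, echocardiography is repeated, and a clinical evaluation takes place monthly. So it would be wrong to say that nothing bearing on harm is compared. None of these records adverse events.
- **The background reports no excess of side effects with DPP-IV inhibitors over control groups.** The titles of the reviews and analyses cited there concern type 2 diabetes or its treatment. The statement does not replace recording events in prediabetes.
- **The rationale is efficacy.** The Justification remarks that "in some of these studies the doses used are frequently associated with the appearance of side effects", and a reader might infer that the combination is justified by fewer side effects. It is not. The reason given is additive pathophysiological effect with cardiovascular protection, and the stated aim of low doses is preventing diabetes and its complications. Nor could a low-dose tolerability premise be tested here, because metformin is 1700 mg/day in both arms and there is no higher-dose arm. Only the effect of adding linagliptin can be compared.
- **The trial is too small for safety.** This is true for testing, as the power figures show. It does not argue against counting events.
- **Other text may cover it.** The protocol commits to good clinical practice standards, and the removed consent pages may mention side effects. Neither would supply an outcome that the objectives, variables, visits and analysis all lack.

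**Conclusion.** The concern holds in a limited form. The plan specifies no recording or between-arm tabulation of adverse events or intolerance, and its elimination criterion is not reconciled with its intention-to-treat analysis. The trial as written would therefore give no adverse-event or intolerance comparison for the added drug.

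Correcting this yields description, not a powered safety test. An arm of 17 with no events is still compatible with a true rate up to 16%. Power is 23% to 30% by chi-square for the contrasts considered. All event rates used are assumptions, since the documents give none. It also cannot be said that event data would exist and merely go unreported, because the visits do not name adverse events as something to record.

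This should be changed, because it is inexpensive and cannot be repaired after follow-up ends.

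**What to change.** 1. Add a secondary objective and outcome: adverse events, and discontinuation for intolerance, by arm.
2. Record them at each monthly visit already scheduled: event, date, severity, action taken.
3. Reconcile the Elimination section with the Statistic analysis section. Define both analysis sets, and state that patients with intolerance remain in the intention-to-treat set and count as having an event. This concerns the analysis only; the clinical handling of intolerance is left as it is.
4. Tabulate, in all randomised patients who took at least one dose, the number with at least one event and the discontinuations by reason, per arm, with the risk difference and an exact 95% confidence interval.
5. State that the table is descriptive and not powered, and give the upper bound wherever an arm has zero events (16% for 0/17, 19% for 0/14).

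The cost is one case report form page at existing visits and one table. No extra visits or patients are needed.
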